#### 3.2 Secondary Endpoints

The key secondary endpoints are:

- Objective response rate defined as the percentage of patients whose best response is CR or PR as assessed by central radiology using mRECIST, version 1.1.
- Overall survival defined as the time from date of randomization to death due to any cause.

Additional secondary endpoints include:

- All individual EORTC QLQ-C30 scores, eg, physical functioning score, pain score, role functioning score, appetite loss score, etc.
- Adverse events, serious AEs (SAEs), and changes in safety laboratory parameters, 12-lead ECG evaluations, and ECOG PS. The intensity of AEs will be assessed by the NCI CTCAE, version 5.0.
- Response as assessed by Investigator per mRECIST, version 1.1. and assessed by central radiology per Choi criteria.
- Disease control is defined as the rate of CR, or PR of any duration, or SD lasting for at least 16 weeks per mRECIST, version 1.1.
- Duration of response defined as the time from first documentation of tumor response to disease progression or death due to any cause.
- Plasma drug concentration at specified time points.
- Abdominal pain as measured by a numeric rating scale (0-10).

■ [REDACTED]

[REDACTED]

■ [REDACTED]

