- s Liver function tests (ALT, AST, alkaline phosphatase, total bilirubin (direct bilirubin if total is > ULN) should be measured every 4 weeks. On even-numbered cycles, when a study visit is not required, these tests should be done locally, and any clinically significant abnormalities should be entered as adverse events, and laboratory values should be entered in unscheduled laboratory eCRF.
- t Tumor imaging will be done at Screening and then every 8 weeks ( $\pm$  1 week) from Cycle 1 Day 1 until disease progression and will be assessed by central radiology review. Disease response assessments using the Choi criteria will be performed centrally. Note that tumor imaging should occur every 8 weeks regardless of the scheduled treatment cycles ie, if study treatment is interrupted or discontinued for any reason, tumor imaging should continue according to an 8-week schedule until disease progression or death. Computed tomography (CT) with IV contrast of the chest and CT or MRI with IV contrast of the abdomen and pelvis will be performed. CT of the chest is not required after screening unless there were sites of disease in the chest. CT with IV contrast is the preferred imaging modality, unless a site of disease is better evaluated by MRI. If a patient is not tolerant of IV contrast, non-contrast scans may be performed. For each patient, the same method of tumor imaging used at baseline should be used throughout the study.
- u Brain imaging should be performed at Screening, Week 12 ( $\pm$ 1 week), and Week 24 ( $\pm$ 1 week), and should be repeated as clinically indicated, ie, for unexpected neurologic AE. Patients who have been on study for more than 12 weeks should have imaging performed at the next scheduled visit and 12 weeks later ( $\pm$ 1 week).
- v The EORTC-QLQ-C30, [REDACTED] will be completed at scheduled clinical site visits up to EOT. The questionnaires are not required at the EOT visit or after cross-over.
- w Adverse events are to be recorded from the start of study drug administration through the Safety Follow-up Assessment.
- x Serious AEs and concomitant medications are to be recorded from the date of the informed consent signature through the Safety Follow-up Assessment.

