## 7 DESCRIPTION OF STUDY PROCEDURES

### 7.1 Screening

After informed consent, all patients will undergo screening procedures within 28 days before dosing on C1D1 to determine eligibility. Patients may be randomized in the system at any time but must be dosed within 28 days of signing of informed consent.

The following procedures will be performed at the Screening visit:

- Obtain demographic data, including sex, date of birth/age, race, and ethnicity;
- Complete medical history, including a history of GIST and/or other malignancies, prior treatments, the response to each treatment if available, and concurrent illnesses;
- Complete physical examination and a basic neurological assessment, including ECOG PS;
- Vital signs including weight, temperature, pulse, and systolic/diastolic blood pressure. Height will also be measured at Screening;
- 12-lead ECG;
- Obtain plasma sample for exploratory biomarkers and ctDNA mutation testing;
- Clinical laboratory assessment (hematology, coagulation, serum chemistry, and urinalysis);
- Serum pregnancy test (women of childbearing potential only);

- Tumor imaging by CT with IV contrast or MRI (CT is required for the chest and preferred for all body regions unless a site of disease is better imaged by MRI). If a patient is intolerant of IV contrast, CTs may be performed without IV contrast.
- Brain imaging by MRI or CT (MRI is preferred, if available);
- Recording of concomitant medications and SAEs. Concomitant medications and SAEs are to be collected from the date of the informed consent signature through the Safety Follow-up Assessment, while AEs are to be collected from start of study drug administration through the Safety Follow-up Assessment.

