### **7.5 Efficacy Assessments**

#### **7.5.1 Disease Response Assessment**

Blinded central radiology review of disease response or disease progression (per Choi criteria and per mRECIST, version 1.1) will be based on local imaging scans performed at the time points outlined in [Table 2](#). Note that tumor imaging should occur every 8 weeks ( $\pm 1$  week) from Cycle 1 Day 1 regardless of the scheduled treatment cycles ie, if study treatment is interrupted or discontinued for any reason, tumor imaging should continue according to an 8-week schedule until disease progression or death.

Computed tomography with IV contrast of the chest, CT or MRI with IV contrast of the abdomen and pelvis will be performed at Screening. At subsequent timepoints, the abdomen, pelvis, and all other body regions that contained sites of disease (target or non-target) at Screening will be imaged. Computed tomography of the chest is not required if

there were no sites of disease in the chest at Screening. Computed tomography with IV contrast is the preferred imaging modality, unless a site of disease is better evaluated by MRI. If a patient is not tolerant of IV contrast, non-contrast scans may be performed. For each patient, the same method of tumor imaging used at Baseline should be used throughout the study.

Computed tomography and MRI scans will be reviewed locally at the study center, ideally by the same individual for each patient at each time point, and disease response and progression will be assessed per mRECIST, version 1.1. Computed tomography and MRI scans will also be collected and reviewed centrally to provide a central assessment of response and progression, both per mRECIST, version 1.1 and per Choi criteria.

Patients on either treatment arm considered by local assessment to have disease progression shall not discontinue treatment until progression (per mRECIST, version 1.1) has been confirmed by central radiology review. Patients may only cross over from regorafenib treatment to avapritinib treatment if disease progression has been confirmed by central radiology review.

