#### 10.5.3.2.4 Disease Control Rate

Disease control is defined as rate of CR or PR of any duration, or SD lasting for at least 16 weeks per mRECIST version 1.1 from the beginning of treatment. Disease control rate will be analyzed similarly as the ORR.

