## **Avapritinib**

### **Statistical Analysis Plan Study BLU-285-1303**

- All individual EORTC-QLQ-C30 scores, including symptom and function scales, and the global health status score.
- ORR as assessed by Investigator per mRECIST 1.1.
- ORR as assessed by central radiology per Choi criteria.
- DCR is defined as the rate of CR or PR of any duration or stable disease (SD) lasting at least 16 weeks from the date of randomization.
- Duration of response defined as the time from first documentation of tumor response to disease progression or death due to any cause.
- Adverse events, serious AEs (SAEs), and changes in safety laboratory parameters, 12-lead ECG evaluations, and ECOG PS. The intensity of AEs will be assessed by the NCI CTCAE, version 4.03 or 5.0.
- Abdominal pain as measured by a numeric rating scale (0-10).

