**Avapritinib**  
**Statistical Analysis Plan Study BLU-285-1303**

**3.2.4 Duration Derivation**

Unless otherwise specified for a specific panel or variable, duration variables will be derived according to the following rules:

Duration (in days) = [end date – start date +1]

Duration (in weeks) = [end date – start date +1] / 7

Duration (in months) = [end date – start date +1] / 30.4375

Duration (in years) = [end date – start date +1] / 365.25.

Duration variables expressed in units greater than day will be rounded to 1 decimal place.

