### *4.6.3.4 Disease Control Rate*

Disease control rate (DCR) is defined as the proportion of patients with a CR/PR of any duration, or SD lasting for 16 weeks from date of randomization. The response will be assessed per mRECIST 1.1. DCR and its two-sided 95% CI will be estimated for the ITT Population using the exact binomial distribution (Clopper-Pearson).

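### Disease control needs SD of at least 16 weeks, a cut on the nominal Week 16 scan day with no window allowance, and the protocol and SAP start the clock on different dates

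*Protocol*

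**What the plan says.** **Definition.** Protocol Section 10.5.3.2.4 counts CR or PR of any duration, or "SD lasting for at least 16 weeks per mRECIST version 1.1 from the beginning of treatment". The endpoint list in Protocol Section 3.2 has "SD lasting for at least 16 weeks per mRECIST, version 1.1" and gives no start date. SAP Section 1.4.2 has "stable disease (SD) lasting at least 16 weeks from the date of randomization". SAP Section 4.6.3.4 has "SD lasting for 16 weeks from date of randomization", without the words for a minimum. SAP Section 6 states that nothing departs from the protocol's planned analyses.

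**Scan calendar.** Protocol Section 7.5.1 says "tumor imaging should occur every 8 weeks", with a tolerance of one week either side, counted from C1D1. Footnote t of the Schedule of Assessments (Table 2) gives the same tolerance.

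**Gap between the two start dates.** Protocol Section 7.1 says "Patients may be randomized in the system at any time but must be dosed within 28 days of signing of informed consent". No other limit is set on the time from randomization to first dose, so it can run from 0 to about 28 days.

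**Duration.** Unless otherwise specified, SAP Section 3.2.4 counts both end dates: "Duration (in days) = [end date – start date +1]". The disease control sections specify nothing else. Neither document says whether SD ends at the last scan showing SD or at the date of progression.

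**The concern.** Sixteen weeks is 112 days, and the nominal Week 16 scan is on study day 113, so the cut sits almost on the scan day. A permitted scan may be a week early. If SD ends at the last SD scan, a patient who is stable on an early but compliant Week 16 scan and progresses by Week 24 is not controlled. The same disease course scanned a few days later is controlled.

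If SD is instead counted to progression, the error reverses: progression first found on a late Week 16 scan counts as disease control.

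The different start dates add a second problem. One patient can be controlled under one document and not under the other, and the SAP does not disclose the difference. At stake are the level of a named secondary endpoint and whether two analysts following the text would report the same rate.

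**Working it through.** **The plan's own figure.** SAP Table 1 sets the target day for Week 4×X at 28×X + 1. With X = 4 this is 28×4 + 1 = 113, as the table shows. The documents give no planned rate or power for disease control.

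**Permitted scan days.** Week 16 is 112 days after C1D1. One week either side gives 105 to 119 days after C1D1, which is study days 106 to 120: 15 days.

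**Scan days that fail, with SD ending at the last SD scan.** Let *s* be the study day of the scan and *g* the days from randomization to C1D1. Under the SAP formula the duration is *s* from C1D1 and *s* + *g* from randomization. The scan fails if this is below 112.

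| Start date | Failing study days | Count |
|---|---|---|
| C1D1 | 106–111 | 6 of 15 |
| Randomization, *g* = 1 | 106–110 | 5 of 15 |
| Randomization, *g* = 3 | 106–108 | 3 of 15 |
| Randomization, *g* = 5 | 106 | 1 of 15 |
| Randomization, *g* ≥ 6 | none | 0 of 15 |

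**One patient, two answers.** With *s* = 108 and *g* = 6, the protocol gives 108 days (not controlled) and the SAP gives 108 + 6 = 114 days (controlled).

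**Size.** Inputs from SAP Section 1.3 are a regorafenib median PFS of 5 months and a hazard ratio of 0.67. Assumptions of this check are exponential PFS, on-schedule scans, and scan days uniform over the 15-day window.

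- Median in weeks: 5 × 30.4375 / 7 = 21.74. S(t) = 0.5^(t × HR / 21.74).
- Regorafenib: S(8) = 0.7749, S(16) = 0.6004, S(24) = 0.4653.
- Avapritinib: S(8) = 0.8429, S(16) = 0.7105, S(24) = 0.5989.
- Week 16 is the last progression-free scan: 0.6004 − 0.4653 = 0.135 (regorafenib) and 0.7105 − 0.5989 = 0.112 (avapritinib).
- From C1D1, × 6/15: 5.4 and 4.5 points. The between-arm difference moves by 5.4 − 4.5 = 0.9 points.
- From randomization at *g* = 3, × 3/15: 2.7 and 2.2 points. The difference moves by 0.5 points.

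**Alternative reading, with SD counted to progression.** The patients affected are those whose progression is first found at Week 16: 0.7749 − 0.6004 = 0.174 and 0.8429 − 0.7105 = 0.132. From C1D1, study days 112–120 (9 of 15) pass the cut, which gives 10.5 and 7.9 points, a difference of about 2.5. Here the lag makes matters worse: at *g* = 3, 12 of 15 days pass, and from *g* = 6 all 15 do.

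All these point figures are upper bounds. Responders count as controlled regardless and have not been removed, and PFS events include deaths without a scan finding.

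**The case against.** The strongest reply is that little depends on this.

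- **Place in the plan.** Disease control is an additional secondary endpoint outside the PFS-ORR-OS sequence in SAP Section 4.6.1. SAP Section 4.6.3.4 plans only a rate with an exact interval and names no between-arm test, although Protocol Section 10.5.3.2.4 says it is analyzed like ORR. This stands, and it is why the item is minor.
- **Shared schedule.** Both arms have the same calendar and rule, so most of the shift is common to both. This also stands.
- **Start date in the analysis document.** The SAP counts from randomization, and a short lag absorbs the early-scan shortfall. This is true if SD ends at the last SD scan, but the documents fix no lag.
- **Scan clustering.** Table 2 heads the Cycle 3 to 5 visits with ±3 days. If Week 16 scans cluster on study days 110–116, only 2 of 7 days fail from C1D1, and none fail from randomization once the lag is 2 days or more. That is plausible, but footnote t explicitly allows a week either way.
- **Visit windows.** SAP Table 1 gives Week 16 a window of days 100 to 127. SAP Section 3.4 applies it to by-visit summaries such as laboratory values, and the disease control section does not invoke it.

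A reader might infer more than the documents support. SAP Section 4.6.3.4 alone could suggest SD of exactly 16 weeks, but SAP Section 1.4.2 and the protocol say at least 16. Counting elapsed days would give 7 failing days of 15, but SAP Section 3.2.4 counts inclusively, which gives 6. The two sets of point figures must not be added, because they belong to readings that exclude each other.

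**Conclusion.** The point holds as a minor item. The 16-week cut has no allowance for the scan window, the end of SD is undefined, and the two documents start the clock on different dates while the SAP declares no change.

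If SD ends at the last SD scan, scan timing decides at most about 5.4 (regorafenib) and 4.5 (avapritinib) points of the rate from C1D1. From randomization at a 3-day lag it decides about 2.7 and 2.2 points, and none from a 6-day lag. The between-arm difference then moves by about 1 point or less. If SD runs to progression, the fault is that progression first seen on a late Week 16 scan counts as control. These sizes rest on exponential PFS at the plan's figures, uniform scan days and assumed lags.

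Only patients whose status turns on the Week 16 scan are affected, not responders or those still stable at Week 24. A reader might infer a threat to the trial's error rate, power or main conclusion. The documents do not support that, because no alpha or sample size depends on this endpoint.

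**What to change.** 1. Use randomization as the start date in both documents, and list the change in SAP Section 6.
2. Define disease control as CR or PR, or central SD with no earlier progression at the scheduled Week 16 assessment within its window (at least 105 days after C1D1) or at a later scan.

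The scan tolerance stays tied to C1D1 because the imaging calendar runs from there. Applying 105 days to a clock that starts at randomization would stack the tolerance on top of the lag: with a 14-day lag, an unscheduled scan 91 days after C1D1 would qualify. Under the proposed rule no compliant Week 16 scan is rejected, progression found at Week 16 never counts as control, and a Week 8 scan (at most 63 days after C1D1) cannot qualify.

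The cost is an edit to the disease control sections of both documents and to SAP Section 6, best made before database lock. It is more than a wording change: for the earliest permitted scans the effective minimum SD duration becomes about 15 weeks from C1D1, and the documents should say so.

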#### 10.5.3.2.5 Duration of Response

Duration of response (CR or PR) is calculated from the date of initial documentation of a response to the date of first documentation of PD or death due to any cause. Censoring rules for DOR will be similar to those for PFS.

The Kaplan-Meier method will be used to descriptively summarize DOR. No inferential statistics will be performed.

[REDACTED]

[REDACTED]

[REDACTED]

[REDACTED]

[REDACTED]

#### **10.5.4 Exposure and Safety Analyses**

A summary of study drug exposure, including total dose, duration of treatment, dose intensity, and the proportion of patients with dose modifications will be summarized by treatment arm. Reasons for dose modifications will be listed by patient and summarized.

Safety will be evaluated by the incidence of AEs, causality, intensity, seriousness, and type of AEs, and by the patient's vital signs, ECOG PS scores, clinical laboratory test results, and ECG data.

Concomitant medications will be listed by patient and will be summarized by treatment arm.

All safety data will be summarized by treatment arm for the safety population.

##### **10.5.4.1 Adverse Events**

Summary tables and listings for AEs will include TEAEs, where an AE is defined as any TEAE that occurred between the first dose of a study drug through 30 days after the last dose of any study drug. The incidence of TEAEs (new or worsening from Baseline) will be summarized according to the Medical Dictionary for Regulatory Activities (MedDRA) by system organ class and/or preferred term, intensity (based on NCI CTCAE version 5.0 grading as assessed by the Investigator), seriousness, and relation to study treatment. The following summaries will be produced:

- All AEs
- AEs leading to dose modifications
- Treatment-related AEs
- Grade 3 or higher AEs
- Grade 3 or higher treatment-related AEs
- Most commonly reported AEs (ie, those events reported by  $\geq 10\%$  of patients in either treatment group)
- SAEs
- Treatment-related SAEs
- Discontinuations due to AEs

By-patient listings will be provided for on-treatment deaths (on-treatment is defined as the period starting from the first dose to 30 days after the last dose), AEs, SAEs, and AEs leading to discontinuation of treatment.

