## 9.8 Adverse Event Electronic Data Capture

All AEs, including SAEs, are to be accurately recorded on the AE page of the eCRF. Information to be recorded in the description of each AE (serious and non-serious) includes:

- A medical diagnosis of the event (If a medical diagnosis cannot be determined, a description of each sign or symptom characterizing the event should be recorded.)
- The date of onset of the event
- The date of resolution of the event
- Whether the event is serious or not
- Intensity of the event (see [Section 9.2](#))
- Relationship of the event to study drug (see [Section 9.3](#))

- Action taken: none; change in the study drug administration (eg, temporary interruption in intervention); drug treatment required; nondrug treatment required; hospitalization or prolongation of hospitalization required (complete SAE page); diagnostic procedure performed; patient discontinued from the study (complete End of Study visit)
- Outcome: patient recovered without sequelae; patient recovered with sequelae; event ongoing; patient died. If this occurs, notify the Medical Monitor immediately, and complete the SAE form.

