## **Avapritinib**

### **Statistical Analysis Plan Study BLU-285-1303**

- regorafenib to avapritinib (“rego to ava”) – Data collected during the extended study treatment period only from patients randomized\* to regorafenib. During this period, patients are treated with avapritinib after crossing over from regorafenib.

\*For analyses using the Safety Population, patients will be grouped based on the study drug actually received during the main study treatment period rather than the study drug they were randomized to.

Safety, laboratory, exposure, compliance, dose modification, concomitant medications, and major protocol deviation analyses will be presented using the 4 groups above.

Efficacy analyses will be presented using 2 groups (avapritinib, regorafenib).

Analysis populations, patient dispositions, baseline or demographic characteristics, patients by country by site, medical history, and prior therapies for the underlying malignancy will be presented using 3 groups (avapritinib, regorafenib, total).

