#### **4.7.1 Adverse Events**

Adverse Events will be analyzed using treatment-emergent adverse events (TEAEs). The TEAE definition is dependent on the study period (e.g., main study treatment period) reported. An AE is considered a TEAE for a specified study period if the AE occurs during or after administration of the first dose of study drug from the same study period through up to the earlier of the last dose of study drug in that period + 30 days or the day before the start of crossover/extended treatment.

Adverse Event refers to TEAEs unless otherwise specified throughout this document. All AEs will be coded using MedDRA version 18.1. The severity will be graded using the National Cancer Institute (NCI) Common Terminology Criteria for Adverse Events (CTCAE), version 4.03 (patients enrolled before protocol amendment 2) and 5.0.

A patient experiencing multiple AEs under the same PT or SOC will be counted only once for that PT or SOC by maximum severity. If a patient experiences the same AE more than once with more than one causal relationship to study drug, the strongest causal relationship to study drug will be given precedence. Any missing severity, causality, or outcome will not be imputed and classified as 'Missing'. Detailed imputation rules for missing AE dates are in [Section 7.1](#).

The number of patients with at least one AE will be summarized ([Table 4](#)). The following tables summarize incidences of various aspects of AEs and serious adverse events (SAEs):

1. AE Summary (including all subsequent items)
2. AE by PT
3. AE by SOC and PT
4. AE related to study drug by PT
5. AE related to study drug by SOC and PT
6. SAE by PT
7. SAE by SOC and PT
8. SAE related to study drug by PT
9. SAE related to study drug by SOC and PT
10. Grade 3/4/5 AE by PT
11. Grade 3/4/5 AE by SOC and PT
12. Grade 3/4/5 AE related to study drug by PT
13. Grade 3/4/5 AE related to study drug by SOC and PT
14. AE by PT and NCI CTCAE Grade
15. AE by SOC, PT, and NCI CTCAE Grade

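### The SAP's period-specific TEAE rule omits worsening, so an AE that starts on regorafenib and worsens after crossover can be missing from the crossover safety tables

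*Protocol*

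**What the plan says.** Protocol section 10.5.4.1 sets one window for the whole study, "between the first dose of a study drug through 30 days after the last dose of any study drug", and within it: "The incidence of TEAEs (new or worsening from Baseline) will be summarized". It has no split by treatment period and no separate crossover column.

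SAP section 4.7.1 splits the study into periods: "An AE is considered a TEAE for a specified study period if the AE occurs during or after administration of the first dose". The dose meant is the one that opens the period in question. The window closes at "the earlier of the last dose of study drug in that period + 30 days or the day before the start of crossover/extended treatment". There is no worsening clause. A patient with several events under one term is "counted only once for that PT or SOC by maximum severity". The SAP does not say whether that maximum is confined to grades reached inside the period.

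SAP section 3.2.7 defines the rego-to-ava column as "Data collected during the extended study treatment period only" from patients randomized to regorafenib, and the regorafenib and avapritinib columns as main-period data. SAP section 3.2.2 ends the main period at CC1D1, the first dose after crossover or after continuation past centrally determined progression. SAP section 3.2.5 defines a rebaseline for crossover patients.

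Among the items recorded for each AE, protocol section 9.8 lists an onset date and "Intensity of the event", each once. It does not say what happens when the grade later rises. SAP section 6 reports no change from the protocol's analyses.

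**The concern.** Crossover patients start avapritinib 7 to 28 days after their last regorafenib dose, so some regorafenib-onset events will still be present. If such an event worsens on avapritinib, the safety reader needs to see the worsening in the rego-to-ava column. The protocol's definition includes worsening. The SAP's does not, and the SAP does not declare the difference.

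The same counting rules apply to the special-interest events in SAP section 4.7.2 (cognitive effects and intracranial bleeding) and to the dementia events in section 4.7.3. These are tables where a rise in grade on avapritinib matters most.

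**Working it through.** The plan gives no figure to reproduce. The check compares the two definitions and traces one event through them.

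**Step 1: do the two columns overlap?** Let the first crossover dose fall d days after the last regorafenib dose, with d between 7 and 28 (protocol section 7.6). The main-period window ends at the earlier of day 30 and day d − 1, that is, between day 6 and day 27. The day-before-crossover limit therefore always applies first, and each onset date falls in one column only.

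**Step 2: what does occurrence mean?** The SAP does not use the word onset. Its date imputation (section 7.1.1) places partial AE start dates relative to the first dose date, which makes onset the natural reading. The other reading is presence in the period. That would count every unresolved regorafenib event in the crossover column, including those that did not change. The first reading loses worsened events and the second adds unchanged ones, so neither gives new or worsening.

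**Step 3: trace one event.** Take a Grade 1 memory impairment that starts on regorafenib, is ongoing at CC1D1 and reaches Grade 3 on avapritinib.

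| Recording and reading | Regorafenib column | Rego-to-ava column |
|---|---|---|
| (a) One record at highest grade; onset | Grade 3 | Absent |
| (b) New record when the grade rises; onset | Grade 1 | Grade 3 |
| (c) One record with dated grades, columns limited to their period; onset | Grade 1 | Absent |
| (d) Presence in the period | Present | Present |

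The documents do not choose among these. Under onset, the event is lost from the crossover column in (a) and (c), and only (b) keeps it. Post-crossover severity reaches the regorafenib column in (a), and in (d) if a single highest grade is kept.

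**Step 4: would the protocol wording cure it?** Not alone. It compares with Baseline in a single window. A crossover column needs a comparison with the grade at CC1D1, which for crossover patients corresponds to the SAP's rebaseline.

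**Step 5: size.** Neither document gives a crossover rate for this trial or a rate of worsening after crossover. The number who can cross over by the primary analysis can be bounded roughly. Assume exponential PFS, a control median of 5 months, HR 0.67, 230 patients per arm and a common follow-up of 7.5 months.

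- Arm B: 230 × (1 − exp(−7.5 × ln 2 / 5)) = 230 × 0.646 ≈ 149 events.
- Arm A: 230 × (1 − exp(−0.67 × 7.5 × ln 2 / 5)) = 230 × 0.502 ≈ 115 events.
- Total: about 264, matching the planned number.

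Crossover requires centrally confirmed progression, and some of the 149 events are deaths, so on these assumptions at most about 149 patients could have crossed over by then. If all 149 did, each affected patient removes 1/149 ≈ 0.7 percentage points from a rego-to-ava row. If half did (about 75), the figure is 1/75 ≈ 1.3 points. Under (a), each affected patient adds at most 1/230 ≈ 0.4 points to a regorafenib Grade 3 or higher row.

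**The case against.** The strongest case against is that the documents may already separate the grades.

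- **Column definitions.** SAP section 3.2.7 limits the regorafenib column to main-period data, so a Grade 3 reached after CC1D1 should not appear there.
- **Worsening as a new event.** Protocol section 9.1.1 treats worsening of a chronic or intermittent pre-existing condition as an AE in itself. Section 7.6 has post-crossover AEs assessed for relationship to avapritinib only, which fits poorly with one record carried across crossover. The eCRF guidelines mentioned in protocol section 11.5 may settle the matter.
- **Other displays.** Laboratory shift tables, blood pressure by visit and by-patient AE listings would show part of what the AE tables miss.

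Much of this stands. A reader might infer that the worst grade is charged to regorafenib and that the randomized comparison is tilted one way. The documents do not support that. It needs a single-record, highest-grade convention that neither document states, and it sits poorly with the main-period column definition. Under that same convention, an Arm A event that worsens during continuation after progression would raise the main-period avapritinib column in the same way.

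A reader might also borrow the 85% of placebo patients who received open-label regorafenib in the earlier trial described in protocol section 1.1.2. That would be 0.85 × 230 ≈ 196 crossovers, more than the roughly 149 Arm B events expected at the primary analysis.

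The gap in the crossover column remains. Section 9.6.2, on pre-existing conditions, covers disorders present before the AE reporting period, not events that began on regorafenib. No section instructs sites to open a new record when an on-study event worsens. Cognitive effects have no equivalent laboratory display.

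**Conclusion.** The concern holds in a limited form. The SAP drops worsening from the TEAE definition, does not tie the extended period to its own rebaseline, and declares no change from the protocol. On the onset reading, and unless a new record is opened when the grade rises, events that begin on regorafenib and worsen on avapritinib are missing from the rego-to-ava AE, Grade 3 or higher and special-interest tables. Crossover avapritinib toxicity is then understated. The avapritinib-overall column combines both periods and loses nothing.

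Any effect on the randomized comparison depends on how the eCRF stores grades. It could touch regorafenib through crossover and avapritinib through continuation, so its net direction is unknown. The number of patients affected cannot be derived from the documents; the per-patient figures above are only a scale. These tables are descriptive and no hypothesis test is affected. The correction is worth making because the rule as written gives an incomplete safety picture and is cheap to put right.

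**What to change.** - **SAP section 4.7.1, definition.** Count an AE as an extended-period TEAE if it starts on or after CC1D1, or if its grade rises on or after CC1D1 above its grade at that point (the rebaseline for crossover patients).
- **SAP section 4.7.1, severity.** Limit maximum severity in each column to grades reached within that column's period, for both arms.
- **Protocol section 9.8 or the eCRF guidelines.** Record the grade at CC1D1 for every ongoing AE, and enter any later increase as a new or dated record.
- **SAP section 6.** List the change.

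The cost is a few lines of SAP wording, one programming rule and one grade entry per ongoing event at CC1D1. Patients who have already crossed over or continued will need some back-querying, so this should be settled before database lock. A few events will appear in both columns at different grades, which a footnote can explain.
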